1.1 Public Health Burden of Ageing and Primary Osteoporosis

1.1.1 Global and Chinese population ageing: current status and trends

Osteoporosis (OP) is a systemic skeletal disorder characterised by reduced bone mass and microarchitectural deterioration of bone tissue, leading to increased fragility and susceptibility to fracture. The condition predominantly affects postmenopausal women and older men. With accelerating global population ageing, OP has emerged as the third most prevalent chronic disease worldwide, surpassed only by cardiovascular disease and diabetes. According to the World Health Organization (WHO) 2023 report, the population aged 60 years and older has exceeded one billion and is projected to reach 2.1 billion by 2050, representing over 21% of the total global population. This trend is particularly pronounced in high-income countries such as Japan and Italy, where life expectancy exceeds 80 years; however, the pace of ageing is even more rapid in low- and middle-income countries, where healthcare infrastructure remains underprepared [1].

China, the nation with the largest ageing population globally, recorded 264 million residents aged 60 and older (18.70% of the total population) in its Seventh National Population Census, with those aged 65 and above accounting for 14.9%—officially marking the transition to a moderately aged society [2]. Projections indicate that by 2025, the population aged 60 and over will surpass 300 million; by 2033 it will exceed 400 million; and by 2050, older adults will constitute more than one-third of the total population [2].

Key drivers of population ageing include declining fertility rates (the global total fertility rate fell from 4.7 in 1950 to 2.3 in 2023), rising life expectancy (from a global average of 46 years in 1950 to over 70 years in 2023), and the epidemiological transition from infectious to chronic diseases as the primary causes of death [1]. China additionally exhibits a rural–urban ageing inversion: the rural ageing rate (20.7%) exceeds the urban rate (16.2%), compounded by weaker rural healthcare systems that exacerbate health inequalities [3]. This demographic shift directly intensifies the burden of chronic bone metabolic diseases, positioning OP prevention and control as a global public health priority.

1.1.2 Epidemiological profile of primary osteoporosis: prevalence, incidence, and sex differences

Primary osteoporosis is a systemic bone disease characterised by decreased bone mass and microstructural destruction leading to increased bone fragility. Prevalence increases exponentially with age. A 2021 global meta-analysis reported an overall OP prevalence of 21.7% (95% CI: 18.8–25.0%) among older adults, with women (35.3%, 95% CI: 27.9–43.4%) significantly more affected than men (12.5%, 95% CI: 9.3–16.7%) [4]. Marked regional disparities exist: Asia leads at 24.3%, followed by Europe (15.8%) and the Americas (11.2%) [4]. In China, the prevalence of OP among adults aged 50 and over is 19.2%, rising sharply with age: 10.6% in the 50–64 age group and 32.0% in those aged 65 and above, with an especially severe burden among women (51.6% in women aged 65+) [3].

Epidemiological studies reveal three key risk stratification features. First, sex differences: the abrupt decline in oestrogen following menopause accelerates bone resorption, rendering women three times more likely to develop OP than men. International Osteoporosis Foundation (IOF) data indicate that approximately one-third of women aged 50 and over worldwide have OP, with this proportion reaching two-thirds among women aged 90 [5]. Second, geographic inequalities: rural OP prevalence in China (35.3%) significantly exceeds that in urban areas (25.6%), primarily attributable to nutritional deficiencies (inadequate calcium intake), insufficient sunlight exposure (reduced vitamin D synthesis), and limited healthcare access [3]. In India, OP prevalence among low-income women reaches 29%, with osteopenia at 52%, directly linked to protein and calcium deficits [6]. Third, diagnostic deficiency: US NHANES 2017–2018 data show that 69.12% of OP cases remain undiagnosed, with the highest missed-diagnosis rates among men (86.88%) and those aged 50–59 (84.77%) [7]. In China, the awareness rate for OP among those aged 50+ is only 7%, the diagnostic rate 36%, and the therapeutic drug utilisation rate merely 6.5%, constituting a “silent epidemic” [8].

1.1.3 Disease burden of osteoporotic fractures: incidence, mortality, disability, and economic costs

Osteoporotic fractures (OPFs) represent the most severe complication of OP and impose a substantial disease burden. Globally, up to 37 million fragility fractures occur annually among individuals aged 55 and older, equivalent to approximately 70 fractures per minute [9]. Hip fracture, the most lethal form of OPF, carries a one-year mortality rate of 20–24%, a disability rate of 50%, and only 33% of patients regain pre-injury functional capacity [10]. Vertebral fractures, although often occult (approximately 70% are clinically unrecognised), may result

in chronic pain, spinal deformity, and impaired pulmonary function [11].

The economic burden exhibits a “double-peak growth” pattern. Regarding direct medical costs, the United States projects an increase from 1.9 million fractures per year in 2018 to 3.2 million by 2040 (a 68% increase), with associated costs rising from USD 57 billion to over USD 95 billion annually [12]. In the EU 27+2 nations, direct costs totalled EUR 56.9 billion in 2019, with hip fractures accounting for 57%, vertebral fractures 10%, distal forearm fractures 2%, and other fractures 32% [12]. Indirect social costs encompass labour-force losses, long-term rehabilitation expenditures, and the risk of household financial collapse.

Importantly, OPFs demonstrate a “cascade effect”: the risk of secondary fracture triples after the initial event, and 50% of secondary fractures occur within one year [12]. Data from the Chinese “Bone Strength Programme” reveal a cumulative re-fracture rate of 32.7% within five years of the initial OPF, creating a vicious cycle [13].

1.1.4 Limitations and challenges of current prevention and management strategies

Despite continual refinement of OP clinical guidelines, the global management landscape remains characterised by a paradox of “high prevalence with low awareness, low diagnosis, and low treatment.” Structural bottlenecks include the following.

Screening and diagnostic system deficiencies: Dual-energy X-ray absorptiometry (DXA), the gold standard for diagnosis, has extremely low coverage in developing countries. In rural China, DXA device density is one-fifth that of urban areas, compounded by insufficient operator training. The widely used FRAX® tool omits critical factors such as fall risk and vertebral fracture history, resulting in over 30% of moderate-to-high-risk individuals being underassessed. NHANES data confirm that only 12% of high-risk OP individuals have undergone bone density testing [12].

Treatment adherence and safety challenges: One-year discontinuation rates for oral bisphosphonates reach 50%, primarily due to complex dosing regimens (fasting upright administration) and fear of adverse effects (e.g., osteonecrosis of the jaw, with an actual incidence of <0.1%). Denosumab withdrawal triggers a rapid decline in bone mineral density (BMD) and a 50% rebound in vertebral fracture risk. Evidence for individualised regimens in frail elderly patients with polypharmacy (≥ 5 medications) remains scarce.

Healthcare system integration failures: Hospital-to-community referral mechanisms are lacking; continuous management of OP patients in China remains a major challenge. Although

models such as Fracture Liaison Services (FLS) can improve care coordination, their penetration in rural areas is limited. Globally, resource allocation disproportionately favours acute treatment over primary prevention. In China, over 70% of OP-related health insurance expenditure funds fracture surgery, while first-line prevention measures (calcium/vitamin D supplementation, exercise intervention) are minimally or not reimbursed [14]. This “treatment-over-prevention” paradigm represents an unsustainable crisis.

1.2 The Rise of the Community-Based Smart Elderly Care Model

1.2.1 Concept, core elements, and driving forces of smart elderly care

The concept of community-based smart elderly care has evolved through three stages: from “informatisation of aged care” to “intelligent elderly care” and, most recently, to “smart elderly care.” According to China’s Ministry of Industry and Information Technology, smart elderly care comprises sensor network systems and information platforms oriented towards older adults, delivering real-time, efficient, and intelligent services [15]. This definition highlights two key elements: technological architecture and service content.

Architecturally, the system operates across three tiers. The perception layer comprises sensing devices—smart wristbands, fall-detection monitors, and similar instruments—that collect health and activity data. The data-processing layer, exemplified by platforms such as Beijing’s “Smart Elderly Care Cloud Platform,” analyses data and issues alerts. The application layer delivers targeted services—health management, daily living support, and related care—based on analytics outputs. This architecture resolves the information fragmentation and slow responsiveness inherent in traditional care models.

Service innovation spans five domains: health management through continuous monitoring for early risk detection; safety assurance via millimetre-wave radar and related technologies for automated fall detection and emergency response; daily living support coordinated through platforms linking meal delivery, cleaning, and similar services; psychosocial care through age-appropriate social applications and companion robots; and social participation via online learning platforms.

1.2.2 Policy background and practical exploration of community-based smart elderly care in China

The development of smart elderly care in China has been largely policy-driven, progressing through three phases: the pilot phase (2014–2020), initiated by Shanghai’s first local standard;

the systems-building phase (2021–2024), marked by the 14th Five-Year Plan for National Ageing Development and the Elderly Care Service System [15]; and the deepening phase (2025–present), guided by the Opinions on Deepening Reform and Development of Elderly Care Services [16].

Regarding infrastructure, by end-2023 China had 404,000 elderly care institutions and facilities with a combined 8.23 million beds, including 41,000 registered institutions (5.172 million beds, 58.9% nursing-type) and 363,000 community-level facilities (3.058 million beds) [17]. Practical implementations vary by region: Beijing has established over 1,000 “smart elderly care stations” providing telehealth services; Chongqing has installed smart handrails in older residential complexes for safety monitoring; and Guangdong’s community elderly care facilities cover over 70% of rural areas.

China has also accelerated standardisation efforts. In 2024, the Ministry of Industry and Information Technology released the Smart Health and Elderly Care Product and Service Promotion Catalogue (2024 edition), for the first time incorporating AI-based detection devices [18]. In 2025, China led the development of IEC 63310, the first international standard on assistive living robots, published by the International Electrotechnical Commission [19].

1.2.3 Application potential and evidence for mHealth and telerehabilitation in chronic disease management

Technological innovation in smart elderly care encompasses four domains. Health monitoring technologies employ millimetre-wave radar and similar sensors for privacy-preserving surveillance of older adults. Smart terminal technologies feature improved user interfaces with dialect recognition. Data analytics technologies apply algorithms to predict service demand. Robotics technologies have produced exoskeleton-assisted mobility devices, exemplified by the Shenzhen exoskeleton robot.

Service delivery models include six archetypes: enterprise-led platforms, government–enterprise collaborations, government-built/enterprise-operated models, private institutions with government subsidies, self-operated enterprises, and technology-integration models. Particularly noteworthy is the “virtual nursing home” model, which consolidates resources to provide professional services while reducing costs.

Artificial intelligence applications continue to advance. In 2024, Fudan University developed an elderly care large language model incorporating a geriatric-specific corpus that simulates multiple interaction scenarios, addressing the perceived “lack of warmth” in technology-

mediated care.

1.2.4 Opportunities and unresolved issues in applying smart elderly care to osteoporosis management

Despite progress, three principal challenges persist. First, the digital divide: a Ministry of Civil Affairs survey indicates that only 32% of older adults are proficient with smart devices, declining to 18% in rural areas. Second, regional development imbalances: platform coverage exceeds 60% in eastern China but falls below 30% in western regions. Third, funding constraints: 70% of projects depend on government investment, with private capital contributing only 15%.

Deeper issues include technology products misaligned with actual user needs, data security risks, and insufficient cross-sector coordination. Local platforms have yet to coalesce into a nationally unified system, and medical and elderly care data remain siloed. Solutions require three directions: developing simplified, dialect-compatible devices; establishing east–west regional support mechanisms; and exploring novel financing instruments such as special-purpose bonds and a national elderly care data platform.

1.3 Current Evidence and Gaps in Resistance Training

1.3.1 Physiological mechanisms and evidence for the effect of resistance training on bone mineral density

The effect of resistance training (RT) on BMD is supported by multiple experimental and clinical studies. The physiological basis centres on mechanically induced bone remodelling. Following muscular contraction and gravitational loading, bone tissue sustains microdamage that activates osteoblast–osteoclast remodelling. This process is regulated by signalling molecules, among which the Wnt/ β -catenin pathway plays a pivotal role. Mechanical loading activates this pathway, promoting the expression of osteogenic genes and enhancing osteoblast differentiation [20].

Additionally, local tissue releases bone morphogenetic proteins (BMPs) and insulin-like growth factor-1 (IGF-1) following loading, which collectively stimulate bone matrix synthesis and trabecular optimisation. Post-RT increases in serum bone-specific alkaline phosphatase (BALP) and decreases in C-terminal telopeptide of type I collagen (CTX) suggest enhanced bone formation and reduced resorption. Borde et al. (2015), in a systematic review, reported that moderate-to-high-intensity RT significantly improves muscular strength and thereby promotes BMD [21].

BMD improvements exhibit anatomical site specificity, with effects typically more pronounced at weight-bearing sites such as the lumbar spine and femoral neck. Impact-loading exercises (e.g., squats, loaded standing) more readily activate bone remodelling. Protocols employing high intensity ($\geq 70\%$ 1RM), a frequency of two to three sessions per week, and intervention durations exceeding 24 weeks yield the most significant BMD gains. Hu et al. identified Wnt pathway modulation and IGF-1 release as critical mechanisms for maintaining bone homeostasis [22], and RT engages precisely these pathways.

Nonetheless, direct mechanistic evidence derives largely from animal models or small-sample intervention studies. The temporal dynamics and dose–response relationships of Wnt, BMP, and IGF-1 in the training response of older populations remain inadequately characterised by large-scale, long-term randomised controlled trials (RCTs). This evidence gap provides the rationale for the biomarker and mechanistic monitoring planned in the present study.

1.3.2 Evidence for the effects of resistance training on muscle strength, physical function, and fall risk

Decline in muscular strength is a primary contributor to falls, fractures, and functional disability. RT can significantly improve muscle strength, balance, and physical function in older adults, thereby reducing fall risk. Cao et al. (2021), writing in *Ageing Research Reviews*, reported that participants in a progressive RT programme (twice weekly, three sets of 8–12 repetitions at 60–80% 1RM for 12 weeks) demonstrated lower-extremity strength gains of 38.5–45.2%, grip strength improvements of 18.7–22.3%, and a 0.17–0.20 m/s increase in 6-metre gait speed [23].

Strength gains are closely linked to improved motor-unit recruitment efficiency, increased muscle-fibre cross-sectional area, and optimised neural control. Quadriceps strength, in particular, exhibits a significant inverse association with fall risk and is therefore a key target for exercise intervention. Rabinovich et al. reported that following high-intensity RT combined with impact training, quadriceps strength increased by over 35% while five-times sit-to-stand test time decreased by more than 20%, demonstrating clinically meaningful functional improvement [24].

Improvements in physical function are further reflected in SPPB and TUG outcomes. A 2022 meta-analysis of 34 RCTs showed that, compared with health education or usual activity, RT significantly improved gait speed (MD = 0.23, 95% CI: 0.07–0.39), appendicular skeletal muscle mass index (MD = 0.24, 95% CI: 0.08–0.40), and grip strength (MD = 2.75, 95% CI:

1.35–4.15) among older adults with muscle wasting [25]. A 2022 meta-analysis of 14 RCTs demonstrated that ≥ 12 weeks of progressive machine-based RT improved TUG (SMD = -0.62), gait speed (SMD = 0.46), sit-to-stand performance (SMD = -0.92), SPPB (SMD = 0.63), and six-minute walk test (SMD = 0.56) relative to usual activity [26].

RT reduces fall risk through three mechanisms: strengthening of lower-extremity musculature to enhance support, improving proprioception for superior postural control, and accelerating neuromuscular reaction time to shorten the fall-response interval. A 2021 meta-analysis of 14 RCTs showed that lower-extremity RT improved TUG (MD = -1.17 , 95% CI: -1.91 to -0.43), single-leg stance time with eyes open (MD = 3.92 , 95% CI: 2.46 – 5.38), and functional reach distance (MD = 4.85 , 95% CI: 3.07 – 6.63), compared with usual activity [27].

In summary, RT is recommended by international guidelines as a core fall-prevention intervention. The WHO Physical Activity Guidelines for Older Adults (2020) explicitly state that all adults aged 65 and older should engage in muscle-strengthening activities at least twice weekly.

1.3.3 Current research landscape and limitations

Despite robust evidence for the efficacy of RT, critical gaps remain in study design and real-world implementation, particularly regarding long-term effects, community feasibility, adherence, and cost-effectiveness. Most RCTs employ intervention periods of 12 months or shorter, with a notable absence of follow-up studies exceeding two years for adults aged over 75 or those meeting frailty criteria.

Community-based implementation faces multiple challenges. Infrastructure deficits constitute a core barrier; according to the 2023 China Urban–Rural Health Service Survey, only 28% of community centres are equipped for RT, falling below 10% in rural areas. Professional supervision is similarly scarce. With respect to adherence, six-month retention rates in non-trial settings commonly fall below 50%, influenced by transportation barriers, scheduling difficulties, monotonous exercise modalities, and the absence of incentive structures.

In health economics, long-term data supporting the cost-effectiveness of community-delivered RT remain unavailable. Significant inter-individual variation—linked to baseline vitamin D levels, sarcopenia status, and VDR genotype polymorphisms—is poorly accounted for, and systematic models for individualised training parameters are lacking. Integration of smart technologies is still at an early stage; most wearable devices are limited to step counting and heart-rate monitoring without adaptive feedback. The digital divide further constrains the

uptake of technology-enhanced training among older adults.

1.3.4 Key evidence gaps that this study aims to address

Drawing on the foregoing analysis of demographic change, OP burden, RT mechanisms, and existing evidence limitations, this study targets six principal evidence gaps, aiming to construct a scientifically grounded, implementable, and scalable “community-based smart RT intervention model.”

First, the absence of long-term intervention evidence. This study will employ a 20-month tracking design comprising an 8-month active training phase and a 12-month maintenance phase, with systematic observation of BMD and muscle-strength trajectories, particularly among subgroups aged ≥ 75 years and those with a Fried Frailty Index ≥ 3 .

Second, insufficient evidence for community scalability. The study will adopt a “low-equipment-dependency” model centred on elastic-band and bodyweight training modules suitable for home or community settings, supported by a three-tier management hierarchy (professionals–community volunteers–family mutual support) and standardised illustrated and video-guided protocols.

Third, low adherence as a barrier. The study will integrate AI-enabled monitoring (smart wristbands), gamification (reward and incentive systems), and peer supervision to enhance participation, targeting an adherence rate exceeding 70%.

Fourth, the absence of cost-effectiveness data. A health-economics evaluation framework will be established, introducing Markov modelling to community RT research for the first time, to quantify the incremental cost-effectiveness ratio (ICER) and cost–utility ratio (CUA), benchmarked against pharmacological interventions such as zoledronic acid.

Fifth, the lack of smart support-system integration. The study will design a “four-dimensional linked” system architecture encompassing data acquisition (wearable terminals), intelligent analytical feedback (AI algorithm platform), community-setting application (elderly care stations or activity centres), and family interaction mechanisms, with emphasis on age-friendly design including voice guidance, offline functionality, and simplified interfaces.

1.4 Research Objectives and Innovations

1.4.1 Overall research objective

The overarching objective is to validate the comprehensive benefits of “community-based

smart RT” for BMD, muscular function, and quality of life (QoL) among older adults with OP, and to establish a sustainable implementation pathway. Specifically: (a) quantify the effect of 8-month RT on lumbar spine BMD through an RCT, with an expected increase of $\geq 3\%$ (benchmarked against the IOF clinical significance threshold); (b) design a long-term intervention strategy with 8 months of supervised training (twice weekly) followed by 12 months of low-frequency maintenance (once monthly); and (c) develop an integrated smart elderly care system featuring real-time wearable monitoring, AI-driven exercise prescription adjustment, and community-station offline supervision, achieving “data–professional–family” three-tier coordination.

1.4.2 Specific research objectives (corresponding to six sub-studies)

Sub-study 1: A logistic regression modelling study to determine whether baseline grip strength and sedentary time predict BMD response ($\geq 1\%$ improvement) to RT, thereby identifying “responders” for individualised exercise prescription.

Sub-study 2: A dose–response study using generalised additive models (GAM) to analyse the minimum effective frequency of RT and to explore nonlinear relationships between training frequency and BMD/balance function (Berg Balance Scale), identifying threshold effects.

Sub-study 3: A mediation analysis examining whether change in grip strength (Δ HGS) mediates the effect of RT on BMD, providing empirical evidence for the muscle–bone coupling mechanism.

Sub-study 4: An empirical analysis investigating whether prior experience with digital devices and technology acceptance scores are associated with higher training adherence, informing the optimisation of smart elderly care platform design.

Sub-study 5: A clustering and visualisation study of QoL trajectories (SF-36) to identify patterns of change in physical (PCS) and mental (MCS) health dimensions, enabling subgroup-targeted intervention strategies.

Sub-study 6: A micro-level cost-effectiveness analysis calculating the marginal cost per 1% BMD improvement based on actual financial data, constructing a community RT cost-effectiveness evaluation model to support policy and health-insurance alignment.

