1.4.4 Methodological innovations

Small-sample dose–response GAM optimisation: Employs penalised smoothing splines ($k = 3$) to constrain degrees of freedom, stably identifying threshold effects of training frequency on BMD improvement under $n < 100$ conditions, resolving the overfitting problem of conventional regression [Sub-study 2].

Mixed longitudinal trajectory analysis (MLTA): Integrates latent class growth modelling (LCGM) with mixed-effects models to identify QoL change subgroups (e.g., “rapid responders” vs. “slow improvers”) from SF-36 data, enhancing small-sample trajectory classification validity [Sub-study 5].

RCT-embedded micro-costing: Constructs a dynamic “BMD gain–cost” model in a community equipment-sharing scenario, incorporating equipment-sharing cost reduction, long-term fracture-prevention benefits, opportunity costs, and personnel/time costs. Calculates ICER for BMD; Markov modelling projects multi-year cost–utility [Sub-study 6].

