1.4.5 Application innovations

Community RT responder screening tool: A nomogram based on baseline grip strength, sedentary time, and BMI for rapid identification of high-responder populations (BMD improvement $\geq 3\%$; AUC = 0.82), guiding targeted resource allocation [Sub-study 1].

Low-technology smart supervision protocol: A “dual-track supervision model”—digital track (WeChat-based training reminders and video guidance) and manual track (weekly telephone follow-up and periodic home visits by community workers).

Health insurance alignment decision tree: Cost-effectiveness outputs translated into policy pathways based on the ICER-to-GDP ratio: when ICER does not exceed one times per-capita GDP, the intervention enters the basic public health service package; when it exceeds this threshold, supplementary commercial health insurance is required.

Chapter 2 Literature Review and Theoretical Foundations

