3.2 Primary Research Hypotheses (H1–H6)

3.2.1 H1 (Sub-study 1)

Among older adults with primary OP receiving the smart RT intervention, baseline health status and health literacy differentially influence RT response. Specifically, participants with lower baseline BMD but higher eHLQ/technology acceptance scores are more likely to achieve clinically significant BMD improvement ($\geq 3\%$ lumbar spine increase). The rationale is twofold: lower baseline BMD provides greater room for improvement, and higher health literacy and technology acceptance enable more complete understanding and execution of the training protocol.

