4.4 Primary and Secondary Outcome Measures

4.4.1 Primary outcomes (T2)

BMD: Lumbar spine BMD (g/cm^2) measured by DXA (e.g., GE Lunar Prodigy), reported as absolute values and percentage change from baseline. Within-day coefficient of variation for lumbar spine BMD is approximately 1%.

Physical function: SPPB total score (0–12), comprising standing balance, 4-metre gait speed, and five-times chair-stand subtests (each scored 0–4).

Quality of life: SF-36 Physical Component Summary (PCS) and Mental Component Summary (MCS), each scored 0–100.

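### Sub-study 1 dichotomises a continuous DXA change before regression, losing about 36–42% of the information when 30–70% respond, although a continuous model could still give the responder probability

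*Protocol*

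**What the plan says.** Section 1.4.2 of the protocol sets up Sub-study 1 as "A logistic regression modelling study to determine whether baseline grip strength and sedentary time predict BMD response". The method is therefore fixed in the protocol. The outcome is binary, but the cut differs between sections:

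- 1.4.2: "predict BMD response ($\geq 1\%$ improvement) to RT".
- 1.4.5: the screening tool, "A nomogram based on baseline grip strength, sedentary time, and BMI for rapid identification of high-responder populations", uses "BMD improvement $\geq 3\%$; AUC = 0.82".
- 3.2.1 (H1): the target is "clinically significant BMD improvement ($\geq 3\%$ lumbar spine increase").

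H1 places the question "Among older adults with primary OP receiving the smart RT intervention", so the model concerns the trained participants.

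Section 4.4.1 lists lumbar spine BMD at T2 as a primary outcome, "reported as absolute values and percentage change from baseline".

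The text gives no sample size for Sub-study 1. The one figure near it is in 1.4.4, which promises "stably identifying threshold effects of training frequency on BMD improvement under" conditions of n < 100 and labels this for Sub-study 2.

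**The concern.** A responder indicator treats someone just under the cut like someone who lost bone, and someone just over it like someone with a large gain. Whether a predictor tracks the size of the change is then judged from a yes/no variable. That lowers the power to detect the predictors and makes their coefficients less precise.

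A logistic model is also tied to one cut. With 1% in one section and 3% in two others, the number of events and the coefficients depend on which is used. The results are meant to guide individualised prescription (1.4.2) and resource allocation (1.4.5), so imprecise or cut-dependent coefficients would carry into the tool.

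**Working it through.** **Inputs from the protocol.** Logistic regression on a binary BMD response (1.4.2); cuts of 1% (1.4.2) and 3% (1.4.5, 3.2.1); continuous BMD at baseline and T2 (3.3.4, 4.4.1); within-day DXA coefficient of variation about 1% (4.4.1). The protocol gives no power figure for Sub-study 1, so there is nothing to reproduce first.

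**Assumed inputs.** Normally distributed change; two-sided alpha 0.05; correlation r of each predictor with the change 0.2, 0.3 or 0.4; responder proportion 30%, 50% or 70%; analysed n 40, 50, 60, 80 or 99.

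**Step 1: information kept by a cut.** The asymptotic efficiency of a dichotomised normal outcome against the full scale is φ(z)²/[p(1−p)], where p is the responder proportion and z its normal quantile.

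- p = 0.50: 0.3989²/0.25 = 0.637, so about 36% is lost.
- p = 0.30 or 0.70: 0.3477²/0.21 = 0.576, so about 42% is lost.
- p = 0.20 or 0.80: 0.490, so about 51% is lost.

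**Step 2: power per predictor.** Simulation, 1,500 runs per cell. Two independent standard normal predictors each have correlation r with a unit-variance change, so the residual variance is 1 − 2r². The t test from linear regression is compared with the likelihood-ratio test from logistic regression on the cut change. The table gives the loss in points of power over the three responder proportions.

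| n | r = 0.2 | r = 0.3 | r = 0.4 |
|---|---|---|---|
| 40 | 5.6–7.2 | 13.5–17.5 | 20.3–26.3 |
| 50 | 7.9–8.6 | 17.7–21.2 | 19.6–24.6 |
| 60 | 8.0–10.9 | 20.4–24.9 | 15.1–22.1 |
| 80 | 14.6–17.6 | 17.6–24.9 | 9.2–14.6 |
| 99 | 15.9–21.5 | 18.0–25.5 | 5.4–8.2 |

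At r = 0.3 with half responding, power is 50% linear against 37% logistic at n = 40, 61% against 43% at n = 50, and 89% against 71% at n = 99. With Wald tests in the logistic model the losses are larger, about 6–35 points. The Monte Carlo standard error of a single power is at most √(0.25/1500) = 1.3 points.

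**Step 3: effect of the inconsistent cut.** Take the 3% gain expected in 1.4.1 as the mean change and assume an SD of 4%. A 3% cut gives 50% responders. A 1% cut gives Φ((3 − 1)/4) = Φ(0.5) = 69%. About 19% of participants would change class with the section consulted.

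Measurement error also matters. A CV of 1% gives a measured change an SD of √2 × 1% = 1.41%. A person with no true change then passes a 1% cut with probability 1 − Φ(1/1.41) = 24%, and a 3% cut with probability 1 − Φ(3/1.41) = 2%.

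**Step 4: the tool does not need the cut at the fitting stage.** A gain of at least c% means T2 BMD ≥ (1 + c/100) × baseline BMD. With fitted mean m and residual SD s, the probability is 1 − Φ{[(1 + c/100) × baseline − m]/s}. The threshold depends on baseline (1.01 × baseline for a 1% cut, 1.03 × baseline for 3%), but one fitted model serves either cut.

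**The case against.** **The binary target is deliberate.** A reader might infer that the 3% figure only benchmarks the expected mean gain, as in 1.4.1, so that nothing calls for a responder definition. The protocol does not support this: H1 makes a gain of at least 3% the target for the individual participant, and 1.4.5 wants a screening tool. This objection stands. Power per predictor is not the only criterion for such a tool, and no comparison of discrimination or calibration was made here. What remains is that a responder target does not require a responder outcome in the fitted model.

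**The sample size is not known.** A reader might infer from n < 100 and 1:1 allocation (4.1.1) that fewer than 50 trainees enter the model, and so quote one loss for this trial. The documents do not support that. The figure is labelled for Sub-study 2 and could mean trained participants, since training frequency exists only among them. The loss must be shown over a range of n.

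**The loss is not always decisive.** It would go too far to say that the cut decides whether predictors can be detected at all. At r = 0.2 and n = 40–50 both analyses are weak (23–30% linear, 17–21% logistic). At r = 0.4 and n = 99 both are strong (over 99% and 92–94%).

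**The alternative has assumptions.** The derived probability depends on the residual distribution, which is hard to verify in a small sample. This stands and is a reason to keep the logistic model as a supportive analysis.

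**Conclusion.** The point holds as a worthwhile improvement to a nested sub-study. The trial's primary BMD outcome stays continuous and is not affected.

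The loss of about 36–42% of the information at 30–70% responders follows from the cut itself, given a normally distributed change. The power loss of roughly 5–26 points per predictor rests on the assumed r, n, responder proportion and independent predictors; the protocol supplies none of these. The simulation modelled the change directly, as a stand-in for a T2 model adjusted for baseline.

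The AUC of 0.82 in 1.4.5 might be read as a planning effect size. It is stated without derivation for a model not yet fitted, so no figure here relies on it.

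The two cuts contradict each other and must be reconciled under either analysis.

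**What to change.** In 1.4.2 and 1.4.5:

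1. Make linear regression of T2 lumbar spine BMD on baseline BMD and the pre-specified predictors the main model for tests and coefficients. Give one predictor list, since 1.4.2, 1.4.5 and 3.2.1 name different ones.
2. Reconcile the percentage threshold across 1.4.2, 1.4.5 and 3.2.1.
3. Derive each person's probability of reaching that threshold from the fitted mean and residual SD, with the threshold expressed relative to baseline on the T2 scale, and build the nomogram from it.
4. Keep logistic regression on the responder indicator as a supportive analysis.
5. State the check of residual normality and constant variance, with an ordinal cumulative-probability model as fallback.

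The cost is wording, including aligning 3.2.1 with the reconciled threshold. No extra participants, scans or visits are needed. The downside is the reliance on the residual distribution, which items 4 and 5 address.
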